**Table 8: Schedule of Laboratory Assessments**

Local Laboratory Tests	Protocol Section	Screening	Treatment						EOT	Safety Follow-Up	Notes			
			Cycle 1			Cycles 2+								
			Day 1	Day 8 (± 2 Days)	Day 15 (± 2 Days)	Day 22 (± 2 Days)	Day 1 (± 2 Day)	Day 15 (± 2 Days)						
Serum chemistries	Table 9	X	X*	X	X	X	X	X	X	X	* May be performed 3 days before the first dose.			
Hematology*	Table 9	X	X**	X	X	X	X	X	X***	X	* Must be drawn twice a week for the first 2 weeks of study treatment. In addition to Cycle 1 Day 1 and Cycle 1 Day 8, hematology samples should be drawn at Cycle 1 Day 4 ± 1 day and Cycle 1 Day 11 ± 1 day. ** May be performed 3 days before the first dose. *** Must be drawn twice a week for 2 weeks after last dose.			
Lipid panel	Table 9	X	X	X	X	X	X	X	X	X				
Coagulation panel	Table 9	X					X*		X		* Cycle 2 Day 1 and then every 3 cycles thereafter.			
Hepatitis screening	Table 9	X												
Urinalysis	Table 9	X					X*				* Cycle 2 Day 1 and then every 3 cycles thereafter			
Pregnancy test	Table 9	X*	X**						X**		All female subjects of childbearing potential. * Serum ** Urine			
PK plasma (predose)	7.8.1		X	X	X	X	X*				Collect before morning dose of study drug. * Cycle 2 Day 1, only for food-effect testing in Part 2.			
PK plasma TIMED (postdose)	7.8.1.1		X*		X*		X**				* Collect at 0.5, 1, 2, 4, and 6 hours after INCB059872 dose. Excess sample will be used for [redacted] analysis. ** Cycle 2 Day 1 only for food-effect study.			

**Table 8: Schedule of Laboratory Assessments (Continued)**

Local Laboratory Tests	Protocol Section	Screening	Treatment						EOT	Safety Follow-Up	Notes		
			Cycle 1				Cycles 2+						
			Day 1	Day 8 (± 2 Days)	Day 15 (± 2 Days)	Day 22 (± 2 Days)	Day 1 (± 2 Day)	Day 15 (± 2 Days)		30 Days (+5 Days)			
Urine PK	7.8.2				X						Obtain a predose sample and store separately. Provide a complete urine output collection from Hour 0 (starting after morning dose) through 6 hours.		

**Table 9: Local Laboratory Tests: Required Analytes**

Serum Chemistries	Hematology	Urinalysis with Microscopic Examination	Hepatitis Screening	Coagulation
Albumin	Complete blood count, including:	Color and appearance	Hepatitis B surface antigen	Prothrombin time/international normalized ratio
Alkaline phosphatase	
 
• Hemoglobin
 
• Hematocrit
 
• Platelet count
 
• Red blood cell count
 
• White blood cell count
 
• Blast (for hematologic tumor types as applicable)
 
	pH and specific gravity Bilirubin Glucose Ketones Leukocytes Nitrite Occult blood Protein	Hepatitis B core antibody HBV-DNA HCV antibody HCV-RNA	Partial thromboplastin time
ALT				
AST				
Bicarbonate				
Blood urea nitrogen				
Calcium				
Chloride				
Creatinine				
Glucose				
Lactate dehydrogenase				
Phosphate				
Potassium				
Sodium				
Total bilirubin				
Direct bilirubin (if total bilirubin is elevated above ULN)				
Total protein				
Uric acid				
Serum Chemistries	Hematology	Urinalysis with Microscopic Examination	Hepatitis Screening	Coagulation
		Lipid Panel	Subjects With AML/MDS	Pregnancy Testing
		Total cholesterol Triglycerides Low-density lipoprotein High-density lipoprotein	Immunophenotyping Cytogenetics	Female subjects of childbearing potential require a serum test at screening and a urine pregnancy test before the first dose on Cycle 1 Day 1 and at EOT. Pregnancy tests (serum or urine) should be repeated if required by local regulations.
			Subjects With MF	
			JAK-2 mutation status Cytogenetics	

Note: Additional tests may be required, as agreed by investigator and sponsor, based on emerging safety data.

## **6.1. Screening**

Screening is the interval between signing the ICF and the day the subject is enrolled in the study (Cycle 1 Day 1). Screening may not exceed 28 days. Assessments that are required to demonstrate eligibility may be performed over the course of 1 or more days during the screening process.

Procedures conducted as part of the subject's routine clinical management (eg, blood count, imaging study) and obtained before signing of informed consent may be used for screening or baseline purposes provided the procedure meets the Protocol-defined criteria and has been performed in the timeframe of the study (ie, within 28 days of Cycle 1 Day 1). All information associated with eligibility requirements must be entered into the appropriate eCRF pages.

Results from the screening visit evaluations will be reviewed to confirm subject eligibility before enrollment or the administration of study drug. Tests with results that fail eligibility requirements may be repeated once during screening if the investigator believes the results to be in error. For screening assessments that are repeated, the most recent available result before treatment assignment will be used to determine subject eligibility. Treatment should start as soon as possible, but within 3 days after the date of enrollment. Additionally, a subject who fails screening may repeat the screening process 1 time if the investigator believes there has been a change in eligibility status (eg, after recovery from an infection). (Note: For subjects who fail screening but are rescreened, a new subject number will be assigned.)

## **6.2. Treatment**

The treatment period begins on the day the subject receives the first dose of study drug (Cycle 1 Day 1) through the point at which the investigator determines the subject will be permanently discontinued from study drug. Cycle 1 Day 1 must be no more than 28 days after the subject has signed the ICF and no more than 3 days after the date of registration. Dates for subsequent study visits will be determined based on this day and should occur within the specified visit windows noted in [Table 7](#) and [Table 8](#) of the scheduled date unless delayed for safety reasons. At Cycle 1 Day 1, results from screening visit evaluations should be reviewed to determine whether the subject continues to meet the eligibility requirements, as specified in Section 3.

Note: Day 15 visits beyond Cycle 4 may be optional (except for subjects in TG E/E1) per subject overall status and approval by the sponsor medical monitor.

## **6.3. End of Treatment**

When the subject permanently discontinues study drug, the EOT visit should be conducted. If the EOT visit coincides with a regular study visit, the EOT evaluations will supersede those of that scheduled visit, and the data should be entered in the EOT visit in the eCRF. The subject should be encouraged to return for the follow-up visit.

## **6.4. Follow-Up**

### **6.4.1. Safety Follow-Up**

The safety follow-up period is the interval between the EOT visit and the scheduled follow-up visit, which should occur 30 to 35 days after the EOT visit (or after the last dose of study drug if the EOT visit was not performed). Note that subjects will be required to submit to twice weekly blood draws in the 2 weeks after the last dose of study drug.

Adverse events and SAEs must be reported up until at least 30 days after the last dose of study drug, the date of the follow-up visit, or until toxicities resolve, return to baseline, are deemed irreversible, or the subject initiates a new anticancer treatment, whichever occurs first.

Reasonable efforts should be made to have the subject return for the follow-up visit and report any AEs that may occur during this period.

If a subject is scheduled to begin a new anticancer therapy before the end of the 30-day safety follow-up period, the safety follow-up visit should be performed before new anticancer therapy is started.

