#### **Study Schedule/Procedures:**

Subjects will have regularly scheduled study visits at the clinical site as part of a 28-day cycle. Study visits are as follows:

- Screening: Day -28 through Day -1
- Cycle 1: Day 1, 4, 8, 11, 15, 22
- Subsequent cycles: Day 1 ( $\pm$  2 days; note that Day 1 must be a day with INCB059872 treatment) and Day 15 ( $\pm$  2 days)
- End of treatment: Subjects must be seen and have blood drawn 2 times per week for 2 weeks after last dose.
- Safety follow-up: 30 days (+ 5 days) after the EOT visit or last dose of study drug if EOT visit not performed (or until toxicities resolve, return to baseline, are deemed irreversible, or the subject receives another anticancer therapy, whichever is shorter).

- Follow-up for disease status (only for subjects who discontinue for reasons other than disease progression).

Laboratory tests for safety

Study visits will include sample collection for hematology, chemistry, coagulation, lipid panel, and urinalysis. Additionally, the screening visit will include serology and fertility/pregnancy testing.

Laboratory tests for PK

Pharmacokinetic [REDACTED] samples will be collected at planned visits and shipped to the sponsor or designee for analysis.

Clinical assessments

Adverse event assessments, vital signs, ECG, physical examination, ECOG performance status, and disease response assessments will be performed by the investigative site.

An objective assessment of disease status will be performed as screening, appropriate to the malignancy type (eg, CT or MRI, bone marrow biopsy/aspirate, peripheral blood, as applicable by tumor type).

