### 5.5.2. Withdrawal Procedures

In the event that the decision is made to permanently discontinue the study drug, the last date of the last dose of study drug and the reason for subject withdrawal will be recorded in the eCRF. In addition, the following steps should be followed (Note: These visits are described in Section 6):

- The study monitor or sponsor must be notified.
- The reason(s) for withdrawal must be documented in the subject's medical record and in the eCRF.
- The EOT visit should be performed.
- The date of the EOT visit should be recorded in the IRT.
- Subjects must be followed for safety until the time of the follow-up visit or until study drug-related toxicities resolve, return to baseline, are deemed irreversible, or initiation of a new anticancer treatment, whichever occurs first.

If the subject discontinues study treatment and actively withdraws consent for collection of follow-up data (safety follow-up or disease assessment), then no additional data collection should occur; however, subjects will have the option of withdrawing consent for study treatment but continuing in the follow-up period of the study for safety/efficacy assessments.

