#### **8.1.2. Reporting**

Adverse events that begin or worsen after informed consent should be recorded on the Adverse Events form of the eCRF. Conditions that were already present at the time of informed consent should be recorded on the Medical History form in the eCRF. Monitoring for the occurrence of new AEs should be continued for at least 30 days after the last dose of study drug. Adverse events (including laboratory abnormalities that constitute AEs) should be described using a diagnosis whenever possible rather than by individual underlying signs and symptoms. When a clear diagnosis cannot be identified, each sign or symptom should be reported as a separate AE.

The term "disease progression" should be recorded as an AE/SAE only if there are no other identifiable AEs/SAEs associated with the disease progression at the time of reporting. For events associated with disease progression, the relevant signs and symptoms should be reported using a diagnosis whenever possible rather than individual underlying signs and symptoms. When a clear diagnosis cannot be identified, each sign or symptom should be reported as a separate AE. If the events resulting from disease progression meet the criteria for an SAE (eg, resulted in hospitalization, a life-threatening event, or death), the specific events(s) should be reported as an SAE(s) as described in Section 8.3.2. In both cases (ie, AEs or SAEs related to disease progression), it should be indicated that each event (reported as a diagnosis or as signs and symptoms) is related to disease progression on the Adverse Events form of the eCRF.

The severity of AEs will be assessed using CTCAE v4.03 Grades 1 through 4. The CTCAE v4.03 severity of Grade 5 will not be used; AEs resulting in death will be graded accordingly using Grades 1 through 4 and have the outcome noted as fatal. If an event is not classified by CTCAE the severity of the AE will be graded according to the scale below to estimate the grade of severity:

Grade 1	Mild; asymptomatic or mild symptoms; clinical or diagnostic observations only; intervention not indicated.
Grade 2	Moderate; minimal, local, or noninvasive intervention indicated; limiting age-appropriate activities of daily living.
Grade 3	Severe or medically significant but not immediately life-threatening; hospitalization or prolongation of hospitalization indicated; disabling; limiting self-care activities of daily living.

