### **8.3.2. Reporting**

Every SAE, regardless of suspected causality (eg, relationship to study drug(s) or study procedure or disease progression), occurring after the subject has signed the ICF through the last study visit (or 30 days after the last dose of study drug, whichever is later) must be reported to the sponsor (or designee) within **24 hours** of learning of its occurrence, unless otherwise specified by the Protocol. Any SAEs occurring more than 30 days after the last dose of study drug should be reported to the sponsor or its designee only if the investigator suspects a causal relationship to the study drug.

Information about all SAEs is collected and recorded on the Adverse Event form of the eCRF. The investigator must assess and record the causal relationship of each SAE to the study treatment.

The investigator must also complete the Incyte Serious Adverse Event Report Form, in English, and send the completed and signed form to the sponsor or designee within 24 hours of becoming aware of the SAE. The investigator must provide a causality assessment, that is, assess whether there is at least a reasonable possibility that the SAE is related to the study treatment: suspected (yes) or not suspected (no). Refer to the Incyte Reference Guide for Completing the Serious Adverse Event Report Form.

The contact information of the sponsor's study-specific representatives is listed in the investigator manual provided to each site. The original copy of the SAE Report Form and the confirmation sheet must be kept at the study site.

Investigational site personnel must report any new information regarding the SAE within 24 hours of becoming aware of the information in the same manner that the initial SAE Report Form was sent. Follow-up information is recorded on an amended or new SAE Report Form, with an indication that it is follow-up to the previously reported SAE and the date of the original report. The follow-up report should include information that was not provided on the previous SAE Report Form, such as the outcome of the event (eg, resolved or ongoing), treatment provided, action taken with study drug because of the SAE (eg, dose reduced, interrupted, or discontinued), or subject disposition (eg, continued or withdrew from study participation). Each recurrence, complication, or progression of the original event should be reported as follow-up to that event, regardless of when it occurs.

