### **9.2. Adverse Events**

#### **9.2.1. Adverse Event Definitions**

A TEAE is any AE either reported for the first time or worsening of a pre-existing event after the first dose of study treatment (until 30 days after the last dose of study treatment). Analysis of AEs (as discussed below) will be limited to TEAEs, but data listings will include all AEs regardless of their timing in relation to study treatment administration.

Adverse events will be tabulated by MedDRA PT and SOC. Severity of AEs will be graded using the NCI CTCAE version 4.03. The CTCAE reporting guidelines and grading details are available on the Cancer Therapy Evaluation Program website.

The subset of AEs considered by the investigator to be related to study treatment will be considered to be treatment-related AEs. If the investigator does not specify the relationship of the AE to study treatment, the AE will be considered to be treatment-related. The incidence of AEs and treatment-related AEs will be tabulated. In addition, SAEs will also be tabulated.

Any missing onset date, causality, or severity must be queried for resolution. Unresolved missing causality and severity will be handled according to the following rules:

- An unresolved missing causality will be considered treatment-related.
- An unresolved missing severity will be identified as an unknown severity.

For purposes of analysis, all AEs will be considered TEAEs unless the AE can unequivocally be defined as not treatment-emergent.

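### Protocol 6.4.1 lets AE and SAE reporting close before day 30, in conflict with its own minimum, with Protocol 8.1.2 and 8.3.2, and with the SAP's 30-day TEAE window

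*Protocol*

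**What the plan says.** **Early-stop text in the Protocol**

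- Section 6.4.1 opens with a minimum, followed by the date of the safety visit: "Adverse events and SAEs must be reported up until at least 30 days after the last dose of study drug, the date of the follow-up". It then adds resolution, return to baseline or irreversibility of toxicities, and closes with "or the subject initiates a new anticancer treatment, whichever occurs first". The rule covers AEs and SAEs alike.
- Section 6.4.1 also says that, when new therapy is planned inside the 30-day period, "the safety follow-up visit should be performed before new anticancer therapy is started".
- Section 5.5.2 follows subjects for safety until the follow-up visit or until drug-related toxicities resolve, return to baseline, "are deemed irreversible, or initiation of a new anticancer treatment, whichever occurs first".
- The Synopsis (Study Schedule/Procedures) has the same idea for safety follow-up: "or the subject receives another anticancer therapy, whichever is shorter".

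**Full-window text**

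- Protocol 8.1.2: "Monitoring for the occurrence of new AEs should be continued for at least 30 days after the last dose of study drug". It names no early stop.
- Protocol 8.3.2 requires SAEs "through the last study visit (or 30 days after the last dose of study drug, whichever is later"). Beyond 30 days, only SAEs with suspected causality are to be reported.
- SAP 9.2.1 counts an event as treatment-emergent from first dose "until 30 days after the last dose of study treatment", with no stop at resolution or new therapy.
- Protocol 9.4.3.1 defines a treatment-emergent AE with no end date.

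**The concern.** AE frequency, duration and severity are the primary endpoint in all four Parts (Protocol 2.2.1). The SAP's TEAE tables treat every subject as observed to 30 days after the last dose. If some sites close reporting earlier, those tables mix subjects with full and truncated post-dose observation, and nothing in the planned displays would show which is which. The SAP's default of treating unclear events as treatment-emergent applies only to events that were reported, so it cannot recover missing ones.

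The post-dose weeks also matter for this drug. Section 9.4.3.5 raises a possible platelet rebound after discontinuation. Section 1.6.1 describes one in animals, about 3-fold at its peak at roughly 14 days and back to baseline at about 28 days. Section 5.4.8 says that immune-related events with nivolumab can appear months after the last dose. A stop at toxicity resolution could close AE reporting before such events occur. The twice-weekly blood draws in the first 2 weeks would still give laboratory values, but not necessarily an AE record.

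**Working it through.** **1. Is 6.4.1 consistent with itself?** Read as an earliest-of rule, reporting ends at the minimum of 30 days, the visit, resolution or irreversibility, and new therapy. That minimum can be any day from 0 to 30. Read as at least 30 days, it cannot be earlier than day 30. Both cannot hold for a subject who meets a trigger before day 30.

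**2. The rules side by side.** Day 0 is the last dose. The trigger days are chosen only for illustration.

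| Subject | 6.4.1, earliest-of reading | 8.1.2 (AEs) | 8.3.2 (SAEs) | SAP 9.2.1 |
|---|---|---|---|---|
| No early trigger | day 30 | at least day 30 | at least day 30 | day 30 |
| New therapy on day 10 | day 10 at the latest | at least day 30 | at least day 30 | day 30 |
| Toxicities resolved on day 7 | day 7 | at least day 30 | at least day 30 | day 30 |

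The gap to the SAP window is 30 − 10 = 20 days in the second row and 30 − 7 = 23 days in the third. In the first row there is none. The conflict therefore bites only for subjects with an early trigger: new therapy, an early follow-up visit, or resolved toxicities. For SAEs, 6.4.1 takes the earliest date and 8.3.2 the later one.

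**3. Are the start points the same?** The Protocol counts 30 days from the last dose of study drug, the SAP from the last dose of study treatment. SAP 4.1.1 uses the latter term to include ATRA, azacitidine and nivolumab. In Parts 3 and 4 the two dates can differ.

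**4. How much could be lost?** The documents give no share of subjects who reach a trigger before day 30, so this cannot be estimated. What can be checked is how much slack the plan's own safety figures have (Protocol 9.2, SAP 3.3). The chance of seeing at least one toxicity is 1 − (1 − p)^n:

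- Part 2, n = 15, p = 15%: 1 − 0.85^15 = 91.3%, against a stated minimum of 90%.
- Part 4, n = 30, p = 7%: 1 − 0.93^30 = 88.7%, against a stated approximate 90%.

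Both reproduce. Now assume that a fraction f of subjects with the toxicity have it only after an early close, so it goes unrecorded. The effective rate is p(1 − f):

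| f (assumed) | Part 2 | Part 4 |
|---|---|---|
| 0 | 91.3% | 88.7% |
| 5% | 90.0% | 87.3% |
| 10% | 88.6% | 85.8% |
| 20% | 85.3% | 82.3% |

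The Part 2 statement needs p of at least 1 − 0.1^(1/15) = 14.2%, so it fails once f exceeds 1 − 0.1423/0.15 = 5.1%. This is a tolerance, not an estimate of f. A toxicity already recorded on treatment does not count towards f.

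**5. Which decisions use this window?** Dose escalation and MTD use events through Day 28 of Cycle 1 (5.4.3). The Part 2 stopping rule uses Cycle 1 DLTs (4.1.2). Part 4 futility uses response (9.6). None depends on the post-treatment reporting window.

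**The case against.** **Section 8 governs.** Section 7.5.1 sends the reader to Section 8 for AE definitions, reporting and recording, and the AE review row of Table 7 cites 8.1. Many sites will therefore apply the 30-day rule. This stands as a reason why under-reporting is possible rather than certain. It does not remove the conflict: 6.4.1 is itself worded as a mandatory reporting rule, and nothing says that Section 8 prevails over it.

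**The visit comes before new therapy.** Section 6.4.1 places the safety visit ahead of the switch, so subjects who change treatment quickly still get an AE review. That is a real mitigation. It covers events up to the visit, not those between the visit and day 30, and it does nothing for the resolution trigger.

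**8.3.2 allows exceptions.** It has a carve-out for cases the Protocol specifies elsewhere, which might be read as deferring to 6.4.1. The carve-out follows the 24-hour reporting clause, so its reach is unclear, and it does not touch 8.1.2 or the SAP.

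**Stopping at new therapy is a legitimate choice.** Events after a switch are hard to attribute, and the stop recurs in 5.5.2 and the Synopsis, so it may be intended. That is fair. The documents do not show that collection must run through new therapy. They show that the sponsor has not said so consistently.

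**The SAP is not a collection rule.** This is correct. It sets a fixed 30-day limit for classifying reported events. It is neither a minimum nor an instruction to sites. The problem is that the analysis window can be longer than the window that was filled.

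**Conclusion.** The plan is wrong as written. Section 6.4.1 contradicts itself and disagrees with 8.1.2, 8.3.2 and the SAP's TEAE window, and the Synopsis and 5.5.2 share its early stop. Sites that follow 6.4.1 may leave the 30-day window incompletely filled for some subjects.

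A reader might go further in three ways that the documents do not support:

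- That AEs will be under-reported. This depends on which section sites follow, and two pointers favour Section 8.
- That a stated share of the primary endpoint is lost. No document gives the rate or timing of new therapy or of resolution. Any loss is confined to the post-treatment tail, while the endpoint covers all treatment-emergent events.
- That dose or stopping decisions are compromised. Cycle 1 DLT, MTD and futility decisions do not use this window.

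The documentary conflict is certain and its effect is of unknown size. It should be corrected, since the repair is cheap and the endpoint is primary.

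**What to change.** State one AE and SAE collection window. Align the Synopsis, Protocol 5.5.2, 6.4.1, 8.1.2, 8.3.2 and 9.4.3.1, and SAP 9.2.1. Editing 6.4.1 alone would leave the same early stop in the Synopsis and 5.5.2. Specifically:

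1. Remove resolution or irreversibility of toxicities as a trigger that ends collection of new AEs. Keep it, if wanted, only as the end of follow-up for an ongoing event.
2. Keep SAE reporting to at least 30 days, as 8.3.2 already requires.
3. Choose one rule for new anticancer therapy. Either collect AEs through day 30 and flag those that start after new therapy, which needs its start date on the eCRF; or, if new therapy is meant to end AE collection, say so in 8.1.2 and end the SAP's TEAE window there too.
4. Use one term for the start of the 30 days, study drug or study treatment, and define it for Parts 3 and 4.

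The cost is edits in several sections of two documents and, under the first option in item 3, a few more AE entries.
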